3.0 PATIENT ELIGIBILITY

Subjects must meet all of the inclusion and none of the exclusion criteria to be eligible to participate in the study. Study treatment may not begin until a subject is enrolled.

3.1 Inclusion Criteria

- 3.1.1 Newly diagnosed GVHD that meets criteria for Minnesota standard risk (see section 7.0)
- 3.1.2 Ann Arbor 1 GVHD by biomarkers
- 3.1.3 GVHD not previously treated systemically (topical therapies and non-absorbed steroids are allowed)
- 3.1.4 Any donor type, HLA-match, conditioning regimen is acceptable
- 3.1.5 Age 12 years and up (children <18 years must weight 50 kg or more)
- 3.1.6 Patients must be engrafted post-transplant (ANC ≥500/µL and platelet count ≥20,000). Use of growth factor supplementation to maintain neutrophil count is allowed.
- 3.1.7 Direct bilirubin must be <2 mg/dL unless the elevation is known to be due to Gilbert syndrome within 3 days prior to enrollment.
- 3.1.8 ALT/SGPT and AST/SGOT must be <5x the upper limit of the normal range within 3 days prior to enrollment.
- 3.1.9 Signed and dated written informed consent obtained from patient or legal representative.

3.2 Exclusion Criteria

3.2.1 Patients currently being treated with any JAK inhibitor including ruxolitinib

- 3.2.2 Relapsed, progressing, or persistent malignancy requiring withdrawal of systemic immune suppression
- 3.2.3 Patients with uncontrolled infection (i.e., progressive symptoms related to infection despite treatment or persistently positive microbiological cultures despite treatment or any other evidence of severe sepsis)
- 3.2.4 Severe organ dysfunction including requirement for dialysis, mechanical ventilation, or oxygen supplementation exceeding 40% FiO2 within 7 days of enrollment.
- 3.2.5 Creatinine clearance or estimated glomerular filtration rate <30 ml/min as calculated by institutional practice (e.g., Cockcroft-Gault equation, CKD-EPI equation, etc)
- 3.2.6 A clinical presentation resembling de novo chronic GVHD or overlap syndrome developing before or present at the time of enrollment
- 3.2.7 Patients receiving corticosteroids >10 mg/day prednisone (or other steroid equivalent) for any indication within 7 days before the onset of acute GVHD except for adrenal insufficiency or premedication for transfusions/IV meds
- 3.2.8 Patients who are pregnant
- 3.2.9 Patients receiving investigational agents within 30 days of enrollment. However, the Principal Investigator (PI) may approve prior use of an investigational agent if the agent is not expected to interfere with the safety or the efficacy of itactinib
- 3.2.10 History of allergic reaction to itacitinib or any JAK inhibitor

4.0 SUBJECT SCREENING AND REGISTRATION PROCEDURES

Study Schema

Fig 4. Study schema.

To be eligible for this study, patients must have newly diagnosed low risk acute GVHD defined as Minnesota standard risk based on symptoms and Ann Arbor 1 GVHD based on biomarkers (see Appendix A). Patients will be recruited from centers participating in the Mount Sinai Acute GVHD International Consortium (MAGIC) where the procedures for obtaining screening samples for biomarker scoring are already established.

The pre-screening process is outlined in Figure 4 above. Consented patients will be registered into the remote data entry system using a unique study number assigned by the MAGIC DCC. Five mL of serum will be collected from patients after GVHD has been diagnosed and before any systemic

treatment has begun and shipped priority overnight to the Mount Sinai GVHD laboratory for early AM arrival (see MAGIC Sample Collection and Storage manual for shipping procedures). Samples can be received Tuesday through Saturday. Once received in the laboratory, the GVHD biomarkers used to assign the Ann Arbor GVHD risk score will be measured by ELISA using standard technical procedures. Processing, measuring, and confirming the ELISA assay results take 4.5 hours (range 4-6 hours). Once the Ann Arbor GVHD risk score is confirmed by [name] (or [name] in [name] absence), the investigator at the participating center will be notified of the score by telephone and written confirmation by email.

Patients who meet eligibility criteria will begin treatment with the study drug, itacitinib. Patients who do not meet eligibility criteria will be considered screen failures and treated according to local institutional practice.

Patient registration for this trial will be centrally managed by the MAGIC Data Coordinating Center of the Icahn School of Medicine at Mount Sinai as described below:

A potential study subject who has been screened for the trial and who has signed the Informed Consent document will be initially documented by the participating site on the Screening and Enrollment Log provided by the MAGIC Data Coordinating Center (DCC).

It is the responsibility of the local site investigator to confirm patient eligibility for the clinical trial. Confirmation of a high MAGIC GVHD risk score will be provided directly to the identified Primary Site contact from the participating site by [name], [name] or designee. All other eligibility criteria will be provided by the participating site. After patient eligibility has been determined, a copy of the completed Eligibility form will be submitted by the requesting site to the MAGIC Data Coordinating Center by email to [contact] with local site investigator signature and supporting source documentation.

The MAGIC Coordinator, who acts as the registrar, will review the submitted documents and process the registration. An email will be sent by the registrar to the requesting site registrar to confirm patient registration. Patients found to be ineligible for participation after being consented will be considered screen failures, and documented as such in the Screening and Enrollment Log. These patients will not receive study treatment.

5.0 TREATMENT PLAN

5.1 Treatment Dosage and Administration

- 5.1.1 Protocol treatment must start within 4 days of confirmation of Ann Arbor 1 GVHD risk score. For example, a patient who is diagnosed with GVHD skin stage 3 (Minnesota standard risk GVHD) on day 21 post-HCT, is consented on a Monday and has a research sample shipped to the [name] Lab that day, will have their GVHD risk score assigned on Tuesday (day 22). Such a patient must begin study treatment no later than Friday (day 25).
- 5.1.2 Itacitinib will be supplied by Incyte. Each participating site will have a sufficient supply of itacitinib on hand to begin treatment. Additional doses will be shipped to the participating site to complete treatment. See section 9.1 for preparation, dispensing, and administration information.

- 5.1.3 Study treatment will consist of itacitinib 200 mg administered orally daily for a 28 day induction cycle followed by a 28 day maintenance cycle.
- 5.1.4 Missed doses will be made by extending the schedule until all 28 doses (or 56 doses in responding patients) have been administered or ten weeks from first dose, whichever comes first.
- 5.1.5 Subjects who miss more than five consecutive doses of the first 28 doses due to noncompliance will be analyzed for safety but considered inevaluable for efficacy assessment and replaced.

5.1.6 GVHD Prophylaxis Medications

Medications given for GVHD prophylaxis such as cyclosporine, tacrolimus, sirolimus, methotrexate, mycophenolate should be continued at therapeutic doses (according to institutional standards) and adjusted as necessary for renal, central nervous system (CNS) or other toxicity using institutional guidelines. This study allows for changes in GVHD prophylaxis medication (e.g., replacement of cyclosporine with sirolimus for management of posterior reversible encephalopathy syndrome [PRES]) as per institutional standards. GVHD prophylaxis medications will be tapered according to local institutional tapering practices.

5.1.7 GVHD treatment

The preliminary data for this study were generated from patients transplanted at multiple centers with heterogeneous GVHD treatment practices. In order to develop "real world" experience in this study, institutional GVHD treatment practices are permitted unless their use is explicitly prohibited.

Systemic steroid treatment should be started if any of the following criteria are met: GVHD worsens (increase by one or more grade) after 3 days, or failure to respond to treatment within 7 days (for GVHD grade III) or 14 days (for GVHD grade II). The decision to remove a patient from study treatment should be discussed with the site PI. Itacitinib must be stopped when systemic steroid treatment is begun. When systemic steroid treatment is initiated, the minimum starting dose is prednisone (or other steroid form equivalent) 1 mg/kg/day for GVHD that involves only the skin and/or upper GI tract and 2 mg/kg/d for GVHD that involves the lower GI tract and/or liver. Institutional practices can be followed for steroid tapering schedules.

5.1.8 Ancillary therapies

Ancillary/supportive care measures for acute GVHD such as the use of anti-motility agents for diarrhea, including octreotide, is allowed at the discretion of the treating physician. Use of ursodiol to prevent/reduce gall bladder sludging or prevent hepatic transplant-related complications is allowed according to institutional guidelines

5.1.9 Supportive Care Guidelines

All patients should receive the following:

- Transfusion support per institutional practice
- Anti-infective prophylaxis against herpes virus is required but otherwise institutional practice can be followed.
- Anti-infective prophylaxis against *Pneumocystis jiroveci*, bacterial and

fungal infections according to standard institutional guidelines.

• Pre-emptive monitoring and treatment for CMV and EBV infections is required but otherwise institutional practice can be followed.

5.2 Toxicities and Dosing Delays/Dose Modifications

Any patient who receives treatment on this protocol will be evaluable for toxicity. Each patient will be assessed for the development of toxicity according to the Time and Events Table (Section 6.4). Toxicity will be assessed according to the NCI Common Terminology Criteria for Adverse Events (CTCAE), version 4.0.

The dose of itacitinib will not be modified. In the event of a SAE causally related to study drug, itacitinib should be discontinued and the patient will be included in all analyses of safety and efficacy. Up to five doses of itacitinib may be held at investigator discretion for nausea, difficulty swallowing, or other complications unrelated to itacitinib and then restarted.

5.3 Concomitant Medications/Treatments

Concomitant use of other investigational agents is not permitted during the treatment phase of the study without PI approval.

Coadministration of a strong CYP3A4 inhibitor (itraconazole) increased itacitinib exposure inhealthy subjects by approximately 5-fold. Concomitant use of strong CYP3A inhibitors should be avoided if clinically feasible. If coadministration of itacitinib with a strong CYP3A inhibitor cannot be avoided, use of an agent with less CYP3A4 inhibition in a class, for example, posaconazole for fungal infection, or prophylaxis is recommended over other choices like voriconazole or itraconazole. Careful monitoring of hematology parameters and clinical signs and symptoms of itacitinib-related adverse reactions is recommended upon initiation of a strong CYP3A4 inhibitor.

Subjects receiving itacitinib should avoid pomegranates or pomegranate juice, grapefruit and grapefruit juice, all of which are known to inhibit cytochrome CYP3A enzymes and may increase the exposure to itacitinib.

Coadministration of a strong CYP3A4 inducer (rifampin) decreased the plasma exposure of itacitinib in healthy subjects by approximately 80%. Concomitant use of strong CYP3A inducers (such as, but not limited to, phenytoin, rifampin, carbamazepine, and St John's Wort (Hypericum perforatum) should be avoided.

5.4 Other Modalities or Procedures

Patients who have undergone allogeneic HCT are often simultaneously being treated for other conditions and transplant-related complications. Such treatments will be considered distinct from the study drug treatment.

5.5 Duration of Therapy

The duration of protocol therapy on this study is eight weeks (56 doses). Protocol therapy will end after the 56th dose of itactinib has been administered or if any of the following criteria apply:

- Systemic steroid treatment (or any other systemic treatment) for GVHD is initiated **OR**
- Patient voluntarily withdraws from treatment **OR**
- General or specific changes in the patient's condition render the patient unacceptable for further treatment in the judgment of the investigator **OR**
- Ten weeks has elapsed since the first dose of itacitinib

5.6 Off Treatment Criteria

Patients will be removed from receiving the investigational drug when any of the criteria listed in Section 5.5 apply. The reason for ending investigational drug therapy and the date the patient was removed from treatment will be documented in the study record. All patients who discontinue treatment should comply with protocol specific follow-up procedures as outlined in Section 5.7. The only exception to this requirement is when a subject withdraws consent for all study procedures or dies.

5.7 Duration of Follow-Up

Patients will be followed until 1 year post-enrollment, withdrawal of consent or until death, whichever occurs first. HCT patients are followed closely and frequent clinical evaluations are the norm. While the following outlines the minimum frequency of follow-up evaluations, it is anticipated that the majority of patients will be evaluated more frequently.

During the first 4 weeks of participation (i.e., through the last dose of the first cycle of itactinib), patients will be seen at least weekly for assessment of their GVHD. During the second four weeks (i.e., the maintenance cycle of itacitinib), patients should be seen at least every other week, although it is anticipated that most patients will be seen more frequently, i.e., weekly. Patients will be evaluated at least at three, six and twelve months from treatment initiation.

5.8 Off Study Criteria

Patients can be taken off study at any time at their own request, or they may be withdrawn at the discretion of the investigator for safety, behavioral, or administrative reasons. The reason(s) for discontinuation from study will be documented and may include:

- 5.8.1 Patient withdraws consent (termination of treatment and follow-up);
- 5.8.2 Loss of ability to freely provide consent through imprisonment or involuntary incarceration for treatment;
- 5.8.3 Patient is unable to comply with protocol requirements;
- 5.8.4 The subject has any disorder or condition that in the investigator's judgment may impede the participant's participation in the study, pose increased risk to the participant, or confound the results of the study
- 5.8.5 Patient becomes pregnant (pregnancy to be reported along same timelines as a serious adverse event);
- 5.8.6 Termination of the study;
- 5.8.7 Patient completes protocol treatment and follow-up criteria.

Discontinuation of study treatment (such as subsequent to starting systemic steroids) does not remove the patient from other aspects of study participation including providing followup data. Participants will be encouraged to provide this information whether or not they complete the anticipated course of study treatment.

5.9 Patient Replacement

Patients who enroll in the study but do not receive any study treatment will be replaced. Patients who initiate study treatment but miss more than five consecutive doses of the first

28 doses for reasons other than toxicity will also be replaced. The number of patients and reason(s) for replacement will be recorded and will be used to assess the feasibility of the study design. This study will allow up to 20% of patients who start treatment (n=14) to be replaced.

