11.3 Data Analysis Plans

The primary endpoint is the proportion of patients who achieve CR or PR by day 28 of treatment with itacitinib without the addition of any other systemic GVHD treatment including steroids. Death, lack of GVHD response to itacitinib by day 28 of treatment, or initiation of steroid or other systemic immunosuppressive therapy for GVHD will be considered failures for this endpoint. The proportion of patients who achieve CR or PR by day 28 in the study patients will be compared to the historical control rate of 67%.

Secondary outcomes such as cumulative incidence of steroid-refractory GVHD, proportion of patients with maximal grade I, II, III, and IV GVHD by day 28 after starting treatment with itacitinib, cumulative incidence of serious infections, cumulative incidence of hematologic toxicities, cumulative steroid dose over four weeks in patients who fail itacitinib monotherapy, overall survival at 6 and 12 months, cumulative incidence of NRM at 6 and 12 months, relapse rate at 6 and 12 months, and cumulative incidence of chronic GVHD requiring systemic steroid treatment by one year will be estimated and compared to historical controls.

Continuous variables will be summarized using standard summary statistics such as number of observations (n), mean, standard deviation (SD), minimum and maximum values, median, and 1st and 3rd quartiles. Categorical variables will be summarized in frequency tables as counts and percentages.

Cumulative incidence of non-relapse mortality will be estimated by Gray's method⁵³ and relapse will be considered as a competing risk. Disease free and overall survival, defined as the time from the transplantation to death or to last follow-up if alive, will be estimated by the method of Kaplan-Meier and the probability curves and 95% confidence intervals will be provided based on the method of Brookmeyer and Crowley⁵⁴.

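### Sections 5.1.5 and 5.9 share one missed-dose trigger but not one consequence: 5.1.5 drops some treated patients from efficacy, and the status of those caught only by 5.9 is not stated

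*Combined protocol and SAP*

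**What the plan says.** Section 5.1.5 deals with patients who miss more than five doses in a row among the first 28. Those who do so "due to noncompliance will be analyzed for safety but considered inevaluable for efficacy assessment and replaced".

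Section 5.9 uses the same threshold for patients who have started treatment, but defines the reason by exclusion: those who miss that many of the first "28 doses for reasons other than toxicity will also be replaced". It caps replacements at 14 (20% of 70) and says nothing about the analysis.

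Other sections bear on who counts:

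- 5.1.4 has missed doses made up later: "Missed doses will be made by extending the schedule until all 28 doses".
- 5.2 allows short holds: "Up to five doses of itacitinib may be held at investigator discretion for nausea, difficulty swallowing", or for other complications unrelated to the drug. After a drug-related serious adverse event, "itacitinib should be discontinued and the patient will be included in all analyses of safety and efficacy".
- 5.5 lists events that end protocol therapy, among them "Systemic steroid treatment (or any other systemic treatment) for GVHD is initiated" and "Patient voluntarily withdraws from treatment".
- 7.1.1, under its entry on evaluability for response, says that efficacy is assessed from the first itacitinib treatment.
- 7.3 defines an at-least-one-dose set, but for safety and tolerability.
- 11.3 scores these as failures of the primary endpoint: "Death, lack of GVHD response to itacitinib by day 28 of treatment, or initiation of steroid or other systemic immunosuppressive therapy for GVHD". It refers to the study patients without defining the set further.

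**The concern.** The trial has one arm, no blinding and one primary proportion, so the result depends directly on who is in the denominator. The reason for a run of missed doses is classified after treatment has begun, by staff who can see how the GVHD is doing. A patient labelled noncompliant under 5.1.5 leaves the efficacy analysis even if that patient died, did not respond or started steroids by day 28, all of which 11.3 counts as failure. For a patient whose reason is neither noncompliance nor toxicity, 5.9 calls for replacement, and nothing says whether the original patient still counts.

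If those removed are mainly non-responders, the observed response rate and the chance of a false claim of non-inferiority both rise.

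**Working it through.** **Inputs.** N = 70, null rate 52%, expected rate 67%, one-sided exact test at 0.04 with 81% power (Synopsis, Statistical Methodology). Two stages of 35, stopping at 19 or fewer responders at stage 1, final boundary 44, 80% power (11.2). The number r of replaced patients who are non-responders is an assumption; the documents give no figure.

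**Step 1: reproduce the plan.**
- Single look: P(Bin(70, 0.52) ≥ 44) = 0.0440 and P(Bin(70, 0.67) ≥ 44) = 0.807. These match 0.04 (to two decimals) and 81%.
- With the stage-1 rule: sum over x = 20 to 35 of P(Bin(35, p) = x) × P(Bin(35, p) ≥ 44 − x). This gives 0.0409 at p = 0.52 and 0.786 at p = 0.67, close to the stated 80%.
- If 44 is itself a futility value, as 19 is at stage 1, success needs 45. The single-look figures are then 0.0257 and 0.732, which do not reproduce the stated power. The main calculation therefore uses 44.

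**Step 2: false-positive rate when non-responders are replaced.** Suppose 70 + r patients are treated, each responding with probability 0.52, and r non-responders are removed. Every responder stays among the 70 analysed, so the rate is P(Bin(70 + r, 0.52) ≥ 44).

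| r | Single look, ≥44 | With stage-1 rule, ≥44 | Single look, ≥45 |
|---|---|---|---|
| 0 | 0.044 | 0.041 | 0.026 |
| 1 | 0.058 | 0.053 to 0.055 | 0.035 |
| 2 | 0.076 | 0.071 | 0.047 |
| 4 | 0.121 | 0.113 | 0.080 |

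For r = 1 the two-stage range depends on the stage in which the replacement falls. For r = 2 and 4 the replacements are split equally between stages.

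**Step 3: sensitivity to the model.** Instead fix the response rate among kept patients at 0.52 × (70 + r)/70 and use Bin(70, that rate). For r = 1, 2, 4 the kept rate is 0.5274, 0.5349, 0.5497, and the single-look result at ≥44 is 0.057, 0.073, 0.113. On this scale, if R = 1, 2 or 4 replaced patients respond at half the rate (26%), the kept rate is ((70 + R) × 0.52 − R × 0.26)/70 = 0.5237, 0.5274, 0.5349. The result is then 0.050, 0.057, 0.073. If replaced patients respond like the rest, the kept rate stays at 0.52 and the false-positive rate at 0.044.

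**Step 4: analysing more than 70 with the cut-off left at 44.** With 71 treated and analysed (35 then 36) and the stage-1 rule, P(success at 52%) = 0.053. The cut-off must therefore move with the number analysed. It also needs a stated target: under the same rule 45 of 72 gives 0.0434, which is below the single-look 0.0440 but above the stated 0.04.

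**Step 5: power if treated patients are kept.** With 70 analysed, z of whom cannot respond and the rest responding at 67%, single-look power is P(Bin(70 − z, 0.67) ≥ 44) = 0.807, 0.760, 0.706 for z = 0, 1, 2. Part of that fall reflects a lower overall rate (z = 2: 68/70 × 0.67 = 0.651). If the all-treated rate is 67%, power stays at 0.81.

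**The case against.** Noncompliance is a subset of reasons other than toxicity. One can read 5.9 as saying who is replaced and 5.1.5 as saying which of them are inevaluable, so no patient receives opposite instructions. That stands: a reader might infer that the sections contradict each other, but the texts show overlap with a gap.

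The gap may also hold few patients. A sixth held dose lies outside what 5.2 permits, and a voluntary withdrawal ends therapy under 5.5, so its untaken doses may not be missed doses at all. That stands too, although the status of anyone in the gap still has to be stated.

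A reader might infer that the plan has no denominator. That is too strong. Sections 7.1.1, 5.2, 5.1.5 and 11.3, with N = 70, together imply treated patients less the 5.1.5 cases. Two things remain open: patients replaced under 5.9 alone, and treated patients without a day-28 assessment.

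Excluding noncompliant patients is, finally, a prespecified choice. It is, but it rests on a post-treatment judgement made without blinding, and it can override the failure rule in 11.3. That makes it a poor primary set and a reasonable sensitivity set.

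**Conclusion.** The point holds as an overlap with unequal consequences, plus a stated exclusion that can bias the primary proportion upward. It should be fixed before analysis.

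The wording mismatch is certain. The size is not: the false-positive figures of 0.058, 0.076 and 0.12 for one, two and four replaced non-responders (about 0.054, 0.071 and 0.113 with the stage-1 rule) are illustrations under an assumed count. They fall back to the design value if replacement is unrelated to outcome.

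Two stronger readings are not supported:

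- Because 5.1.7 stops itacitinib when steroids start, a reader might infer that 5.9 replaces steroid-treated non-responders. Making up missed doses (5.1.4), the end of therapy at steroid start (5.5), continued participation after it (5.8) and failure scoring (11.3) all point the other way. It is a wording risk that one sentence would close.
- A reader might take the cap of 14 as the number of failures likely to be removed. It is only a ceiling on replacements, and the documents say nothing about how replaced patients would respond.

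**What to change.** 1. Merge 5.1.5 and 5.9 into one replacement rule that also states how a replaced patient is analysed.
2. Name all patients with at least one dose of itacitinib as the primary analysis set.
3. State that death, start of steroids or other systemic GVHD therapy, or lack of response is a failure under 11.3, and that such a patient is neither replaced nor removed.
4. State how a treated patient without a day-28 assessment is scored.
5. Report the response rate in the 5.1.5 adherence-evaluable set as a sensitivity analysis.
6. Whether to go on enrolling replacements is the sponsor's choice. If more than 70 are then analysed, recompute the final cut-off for the number treated, under the two-stage design in 11.2 and against the stated 0.04.

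The cost is protocol wording and possibly some power. Single-look power falls from 0.81 to 0.76 or 0.71 if one or two kept patients cannot respond and the others respond at 67%. Nothing is lost if the all-treated rate is 67%. The sponsor should restate the power figure; the trial need not be enlarged.
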